## 15. Research Sites

Our records for the previously approved IRB application indicate that you are conducting research at the following sites:

### UK Sites

- UK Classroom(s)/Lab(s)
- UK Clinics in Lexington
- UK Clinics outside of Lexington
- UK Healthcare Good Samaritan Hospital
- UK Hospital

### Schools/Education Institutions Schools/Education Institutions

- Fayette Co. School Systems \*
- Other State/Regional School Systems
- Institutions of Higher Education (other than UK)

### Other Medical Facilities

- Bluegrass Regional Mental Health Retardation Board
- Cardinal Hill Hospital
- Eastern State Hospital
- Nursing Homes
- Shriner's Children's Hospital
- Other Hospitals and Med. Centers

Correctional Facilities

Home Health Agencies

International Sites

Other:

If the above listed sites are not accurate, go to the Research Sites section of the E-IRB application to update the facilities at which research procedures have been or will be conducted.

**If you are adding a new off-site facility, you may also need to update your E-IRB application Research Description, Research Sites, Informed Consent, and other affected sections as well as any documents which will list the off-site facility.** Documents needing updating may include, but not limited to:

- Consent forms (attachment under Informed Consent section)
- Brochures (attachment under Additional Info section)
- Advertisements (attachment under Research Description section) ;
- Letter of support (attachment under Research Sites section)).

Please revise applicable sections and attachments as necessary.

## 16. Disclosure of Significant Financial Interest

### Disclosure of Significant Financial Interest:

Our records for the previously approved IRB application indicate that you, your investigators, and/or key personnel (KP) have a [significant financial interest \(SFI\)](#) related to your/their responsibilities at the University of Kentucky (that requires disclosure per the [UK administrative regulation 7:2](#)): [①](#)

Yes  No

If you need to update your records, please go to the PI Contact Information section and/or Details for individuals listed in the Study

Personnel section to change your response to the applicable question(s).

## **17. Supplements**

To ensure the IRB has the most accurate information for your protocol you are expected to re-visit the E-IRB application sections and make corrections or updates as needed. At a minimum you are being asked to review the following sections for accuracy:

STUDY DRUG INFORMATION—Please review for accuracy.

STUDY DEVICE INFORMATION—Please review for accuracy.

RESEARCH ATTRIBUTES—Please review for accuracy.

OTHER REVIEW COMMITTEES -- Please review for accuracy.

**PROJECT INFORMATION****0 unresolved comment(s)**

Title of Project: (Use the exact title listed in the grant/contract application, if applicable).

If your research investigates any aspect of COVID-19, please include "COVID19" at the beginning of your Project Title and Short Title

Accelerated Transcranial Magnetic Stimulation (TMS) for Smoking Cessation in People Living with HIV/AIDS (PLWHA)

**Short Title Description**

Please use a few key words to easily identify your study - this text will be displayed in the Dashboard listing for your study.

Accelerated TMS for Smoking Cessation in PLWHA

Anticipated Ending Date of Research Project: 1/31/2024

Maximum number of human subjects (or records/specimens to be reviewed) 4

After approval, will the study be open to enrollment of new subjects or new data/specimen collection?  Yes  No

Are you requesting that the UK IRB serve as the lead IRB for a multi-site study, **OR** that the UK IRB defer review to another IRB? [Click [here](#) for "IRB Reliance" help]

Yes  No

If "Yes," before completing your IRB application, fill out the [Reliance Request Form](#) and submit it to [[contact]](mailto:[contact]).

## PI CONTACT INFORMATION

0 unresolved comment(s)

## Principal Investigator (PI) role for E-IRB access

The PI is the individual holding primary responsibility on the research project with the following permissions on the E-IRB application:

1. Read;
2. write/edit;
3. receive communications; and
4. submit to the IRB (IR, CR, MR, Other Review\*).

If research is being submitted to or supported by an extramural funding agency such as NIH, a private foundation or a pharmaceutical/manufacturing company, the PI listed on the grant application or the drug protocol must be listed as PI here.

Please fill in any blank fields with the appropriate contact information (gray shaded fields are not editable). Required fields left blank will be highlighted in pink after you click "Save".

To change home and work addresses, go to [myUK](#) and update using the Employee Self Service (ESS) portal. If name has changed, the individual with the name change will need to submit a ['Name Change Form'](#) to the Human Resources Benefits Office for entering into SAP. The new name will need to be associated with the individual's Link Blue ID in SAP before the change is reflected in E-IRB. Contact the [HR Benefits Office](#) for additional information.

The Principal Investigator's (PI) contact information is filled in automatically based on who logged in to create the application.

**RISK LEVEL****0 unresolved comment(s)**

Indicate which of the categories listed below accurately describes this protocol

- (Risk Level 1) Not greater than minimal risk
- (Risk Level 2) Greater than minimal risk, but presenting the prospect of direct benefit to individual subjects
- (Risk Level 3) Greater than minimal risk, no prospect of direct benefit to individual subjects, but likely to yield generalizable knowledge about the subject's disorder or condition.
- (Risk Level 4) Research not otherwise approvable which presents an opportunity to understand, prevent, or alleviate a serious problem affecting the health or welfare of subjects.

\*\*"Minimal risk" means that the probability and magnitude of harm or discomfort anticipated in the research are not greater in and of themselves from those ordinarily encountered in daily life or during the performance of routine physical or psychological examination or tests.

**\*\*\*For Expedited and Exempt Applications, the research activities must be Risk Level 1 (no more than minimal risk to human subjects).\*\*\***

Refer to [UK's guidance document](#) on assessing the research risk for additional information.

**SUBJECT DEMOGRAPHICS**

0 unresolved comment(s)

Age level of human subjects: (i.e., 6 mths.; 2yrs., etc.)  to **Study Population:**

Describe the characteristics of the subject population, including age range, gender, ethnic background and health status. Identify the criteria for inclusion and exclusion.

Provide the following information:

- A description of the subject selection criteria and rationale for selection in terms of the scientific objectives and proposed study design;
- A compelling rationale for proposed exclusion of any sex/gender or racial/ethnic group;
- Justification for the inclusion of vulnerable groups such as children, prisoners, adults with impaired consent capacity, or others who may be vulnerable to coercion or undue influence.

Please consider this [FDA Guidance on Enrollment of Participants from Underrepresented Populations in Clinical Studies](#)

Inclusion criteria. Potential participants will be: 1) Patients enrolled in the Bluegrass Clinic; 2) 18-60 years of age; 3) male or female gender 4) Able to read, understand and communicate in English; 5) willing to adhere to the general rules of the Bluegrass Clinic/SMARTClinic/Beyond Birth Clinic; 6) willing and able to abstain from drug use other than Suboxone; 7) exhaled breath on day of study CO < 5 ppm; 8) Stabilized on maintenance buprenorphine if having comorbid opioid use disorder.

Exclusion criteria. Positive pregnancy test for females, traumatic brain injury, history of seizure disorder, history of or current diagnosis of schizophrenia, intracranial metal shrapnel, previous adverse effect with TMS, sub-threshold consistency while performing behavioral tasks, failure to show baseline attentional bias to smoking versus neutral cues.

The main study is not connected to the Bluegrass HIV clinic, SMART clinic or the Beyond Birth Clinic. A person can be enrolled and receiving care at these clinics, and their participation in the research project does not impact their standing in any of these clinics. Participation is truly voluntary in nature.

To modify: A new updated phone script will be attached to this section.

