## Objectives

List your research objectives. Please include a summary of intended research objectives in the box below.

To demonstrate whether four sessions of TBS improves attentional bias and craving in PLWHA smokers compared to four sessions of sham stimulation. We hypothesize 4 sessions of TBS to the left DLPFC will significantly improve attentional bias and craving for smoking cues compared to neutral cues in a population of subjects who are smokers with HIV/AIDS compared to sham stimulation.

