We will recruit 60 subjects from the Bluegrass Care Clinic, SMART clinic and Beyond Birth Clinic. Study members will interface with all providers in these clinics on a daily basis. All providers in these clinics will be provided multiple copies of the business cards. All providers in these clinics will also be informed about inclusion and exclusion criteria for the study, based on which all patients will be screened by them. Initial contact will be made with potential subjects by those having legitimate access to the subjects' identities/information (ie only providers in the clinic). The PI ([name]) and a research assistant will interface with a contact in each of these clinics on a daily basis. Business cards (that list a few study details and a call back number if subjects are interested in the study) will be provided to subjects at each of these clinics by clinic providers. The case manager for this clinic [name] will send an email to all patients from the Bluegrass Care Clinic, with the business card attached and informing them about the study. A draft of the email is attached in the research procedure section. Subjects interested in the study can call the number provided on the business card to express interest in the study. This number belongs to the Patient Oriented and Population Science Shared Resource Facility (POP SRF). The POP SRF headed by [name] will help the study team with phone screening subjects for the study and their recruitment if they fulfill inclusion and exclusion criteria. Members of the POP SRF ([name], [name] and [name]) have also been added to the list of key study personnel. The POP SRF works closely with Markey Cancer Center and they will assist the PI with recruitment. We are able to avail of this assistance since the study is funded by a pilot cancer center grant from Markey Cancer Center (MCC). Once a subject is identified as suitable for the study, the POP SRF will inform [name] via UK email. Subjects will be asked to meet [name]/research assistant either at MRISC or at [name] to get informed consent if they are interested in study participation and fulfill other eligibility criteria for the study. All data collected from phone screening would be entered into RedCap, regardless of whether subjects do or don't fulfill inclusion and exclusion criteria. During screening, subjects will not be coerced to participate in any way.

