#### Modification Request to the research procedures:

An additional two follow-up visits will be added to this study research procedure by the study Principal Investigator [name]. [name]. The research team will follow up with subjects at one-week and two-week intervals with a urine cotinine test (ACCUTEST urine cotinine tests from Janet Pharmacocal) and carbon monoxide testing using Smokerlyzer (Bedfont Scientific Limited). These two follow-up short visits 2-3 minutes will be performed in the SMART clinic lab space. The CUTEST cotinine assay is a qualitative test and indicates the presence or absence of cotinine. Cotinine is a metabolite of nicotine, and these measures will help assess abstinence from cigarette smoking in response to our intervention. The additional follow-up visit details will be incorporated into the informed consent form and in the E-IRB application for IRB further review and approval.

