#### Delay discounting task

Attention bias behavioral activation (ABBA) task using go/no go

Barratt impulsiveness scale (BIS-11)

Tobacco Craving questionnaire (TCQ)

TMS Side effects scale

Treatment acceptability questionnaire (TAQ)

Resting state functional magnetic resonance imaging (fMRI)

Neuroimaging data will be acquired on a Siemens 3-Tesla (3T) PRISMA scanner. A high-resolution (1 cubic millimeter voxels) T1-weighted MP-RAGE structural image will be acquired for each subject. Functional images will be acquired using echo-planar imaging. Hyper-angulated volumes will be acquired with 37 ascending and interleaved slices at an angle 30-degrees to the anterior-posterior commissure to prevent OFC washout. Additional parameters will be similar to those used in other approved neuroimaging protocols in our lab (e.g., a repetition time (TR) of 2 seconds, echo time (TE) of 25 ms, a flip angle of 90 degrees, and functional voxels of size 3.4mm x 3.4mm x 4.0mm). Image preprocessing will be performed in statistical parametric mapping (SPM) 12 software using standard procedures (see [name] et al., 2014). Data from functional scans will be treated similarly to fMRI data in previous studies (e.g., slice-timing corrected, head-motion corrected, warped into MNI standard space, re-sliced to 4 cubic millimeter voxels and smoothed with an 8mm full-width, half-maximum (FWHM) Gaussian kernel).

To modify: An additional two follow-up visits will be added to this study research procedure by the study Principal Investigator [name]. [name]. The research team will follow up with subjects at one-week and two-week intervals with a urine cotinine test (ACCUTEST urine cotinine tests from Janet Pharmacocal) and carbon monoxide testing using Smokerlyzer (Bedfont Scientific Limited). These will be performed in the SMART clinic lab space. The CUTEST cotinine assay is a qualitative test and indicates the presence or absence of cotinine. Cotinine is a metabolite of nicotine, and these measures will help assess abstinence from cigarette smoking in response to our intervention. The additional follow-up visit details will be incorporated into the informed consent form and in the E-IRB application for IRB further review and approval.

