## Digital Data

Personal information of participants (Subjects' age, comorbid medical or psychiatric illnesses, history of substance use, history of traumatic brain injury/loss of consciousness, previous adverse effects with TMS, medication history, duration of treatment with suboxone, urine drug screens, breathalyzer test results) will be stored in an excel sheet on a protected laptop at [name] (In a locked office and behind a protected firewall). The excel sheets containing the personal information will be saved as an encrypted file every time. A data crosswalk of patient/participant name and MRN will be stored separately from deidentified data and any other research data. Any data sharing will be restricted to the de-identified data. Data will be kept for a minimum of 7 years, and electronically destroyed by UK Policy A13-050 and UK Policy A05-055. For the study proper, urine samples will be collected prior to every TMS session to perform drug screening.

Participant data will be stored in an excel sheet on a protected laptop at [name] (In a locked office and behind a protected firewall). The excel sheet containing personal information will be saved as an encrypted file every time new data is entered. A data crosswalk of patient/participant name and MRN will be stored separately from the deidentified data. Any data sharing will be restricted to the de-identified data. Data will be kept for a minimum of 7 years, and electronically destroyed by UK Policy A13-050 and UK Policy A05-055. Urine samples will be collected prior to every TMS session to perform drug screening.

Before recruitment of a subject into the study we will phone screen the subject for seizure disorder, as part of recruitment. We will also screen for previous adverse effects to TMS. Prior to the MRI session, we will also screen for metallic implants/devices in the body. This will also be clarified with the subject.

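### On the visible text, week-1 and week-2 CO and cotinine cannot show abstinence as a response to stimulation: CO is already capped by an entry criterion and no pre-stimulation cotinine appears

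*Combined protocol and SAP*

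**What the plan says.** The Objectives place the hypothesis "in a population of subjects who are smokers with HIV/AIDS compared to sham stimulation", and the project title concerns smoking cessation. The eligibility list under Subject Demographics has eight inclusion items: clinic enrolment, age, gender, English, clinic rules, abstaining from drugs, exhaled CO and buprenorphine stability. The CO item reads "exhaled breath on day of study CO < 5 ppm". It does not say which study day or why. The only smoking-related filter is an exclusion for people who show no baseline attentional bias to smoking cues.

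A modification under Research Procedures adds visits at one and two weeks with urine cotinine and exhaled CO, and states that "these measures will help assess abstinence from cigarette smoking in response to our intervention". Data Collection & Research Materials repeats the addition and says that "The CUTEST cotinine assay is a qualitative test and indicates the presence or absence of cotinine". The day-one assessment lists under Study Design and Research Procedures name no cotinine. The Digital Data text says that "urine samples will be collected prior to every TMS session to perform drug screening" and does not mention cotinine there. The visible text gives no CO cut-off for abstinence.

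**The concern.** A claim that someone became abstinent in response to an intervention needs evidence that the person was smoking beforehand and a measure that can register the change. Here the two biochemical measures fall short for different reasons. CO is required to be low at the eligibility check, so a low value later need not be new. Cotinine is read only as present or absent and has no visible starting value, so a negative result has nothing to be compared with. The second problem does not depend on what criterion 7 was meant to do.

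What is at stake is a secondary result. A participant who is CO-low and cotinine-negative at week 1 or 2 could be reported as a responder when the data show only status at that visit. The Background says that the pilot data will support a grant resubmission, so a misread result could be carried forward.

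**Working it through.** The plan gives no abstinence rate, cut-off or power for this measure, so there is no stated figure to reproduce. The check sets the sections side by side.

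**1. Eligibility.** Inclusion criteria naming current smoking: 0 of 8. The attentional-bias exclusion is a cue-task result, not a smoking history.

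**2. CO.** Let c be the CO level below which a participant counts as abstinent at follow-up; the documents do not state c.
- If c is 5 ppm or higher (an assumption), CO < 5 implies CO < c. Everyone meeting criterion 7 is then already CO-abstinent at that reading (100%). The number who can move from CO-positive to CO-abstinent relative to it is 0, and the measure can only stay the same or worsen.
- If c is below 5 ppm, a change is possible only for people whose criterion-7 reading lay from c up to 5 ppm. The documents give no way to estimate how many.
- In either case a high follow-up CO could still indicate smoking. What is lost is the meaning of a low one.

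**3. Cotinine.** A negative result at week 1 or 2 fits two histories:

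| Before stimulation | Week 1 or 2 | Meaning |
|---|---|---|
| Positive | Negative | Change |
| Negative | Negative | No change |

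Only the second column is visible in the plan, so the two rows cannot be told apart.

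**4. Clinic smoking figures.** The Resources section gives 70% self-reported smoking, 1,700 patients and about 1,073 smokers.
- By percentage: 1 − 0.70 = 30% not smoking.
- By count: (1,700 − 1,073)/1,700 = 627/1,700 = 36.9%.
- The two differ because 0.70 × 1,700 = 1,190, not 1,073; and 1,073/0.70 = 1,533, which suggests a smaller base.

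These figures describe the clinic. They are not rates among people who entered the study.

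**5. Whether a sham comparison could help.** The opening paragraphs of Study Design and Research Procedures describe a crossover, with stimulation on days two and three. Later text in the same sections describes two groups and one stimulation day, and the follow-up modification and modified Payment text fit that description.
- Under the crossover, everyone has had both TBS and sham before follow-up, so abstinence could not be attributed to TBS whatever the baseline.
- Under two randomised groups, baseline status is balanced in expectation. A missing baseline then mainly dilutes the comparison, while individual before-after readings remain unsupported.

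This conflict is a separate issue and must be reconciled in its own right.

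**The case against.** The strongest reply is that the deciding documents are not shown. The phone script is attached to the same section as the eligibility list, and the four-visit timeline is attached elsewhere. Either may hold a smoking question or a baseline test, and the day-one lists are not exhaustive: a later modification adds a day-one blood draw. The intended population is also clear. The title, the Objectives and the benefits text all refer to smoking or tobacco use. The Resources section builds the recruitment pool for the larger grant from smokers only. All of this stands, so the claim is limited to what the visible text can support.

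A reader might go further in three ways, none of which the documents support.
- **That roughly 30% to 37% of participants were non-smokers.** Those are clinic-wide figures. They ignore the attentional-bias exclusion, self-referral to a smoking study and the two other recruiting clinics. Nothing shows that any non-smoker was enrolled.
- **That the phone screen omits smoking.** The statement that "Before recruitment of a subject into the study we will phone screen the subject for seizure disorder, as part of recruitment" sits in a safety paragraph, and its phone-screen sentences also leave out other listed eligibility items. Its silence on smoking shows nothing.
- **That the trial's main result is compromised.** Abstinence is not in the Objectives, and the attentional-bias task's primary variable is fixation time.

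The reply does not remove the gap in the listed criteria. Recruitment text says that clinic providers are "informed about inclusion and exclusion criteria for the study, based on which all patients will be screened by them", so the defining condition belongs in that list. It also leaves the week-1/2 reading without a visible baseline.

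**Conclusion.** The point holds in a limited form and is minor. On the visible text, week-1 and week-2 CO and cotinine describe status at those visits and cannot be read as abstinence produced by the intervention. For cotinine this rests on no pre-stimulation result being visible; an unseen attachment could change that. For CO it rests on criterion 7, whose study day is not specified. The statement that 100% already count as CO-abstinent holds only if the abstinence cut-off is 5 ppm or higher, and no cut-off is stated. No share of non-smokers among entrants can be given; it may be zero.

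The harm is confined to a misread added measure. The attentional-bias and craving objectives are not affected by this point. Enrolment is closed at 4, so for this trial only the reporting can change.

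**What to change.** **For the 4 enrolled participants.** List each person's follow-up CO and cotinine beside the criterion-7 CO, the stimulation received (with its order, if both were given) and recorded smoking status. Smoking status may be in the phone-screen records, since "All data collected from phone screening would be entered into RedCap", or in the stored substance-use history; otherwise write unknown. Make no claim that TBS produced abstinence. Cost: a four-row listing and one limiting sentence.

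**For the protocol text or a follow-on study.**
- Name current cigarette smoking in the inclusion criteria.
- State the purpose and study day of criterion 7, and reconcile it with a population of smokers.
- Run the same cotinine strip on the urine already collected, before the first TMS session, and keep the criterion-7 CO value as baseline.
- Define abstinence as a change from a cotinine-positive baseline, with a CO cut-off stated in advance.

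Cost: eligibility wording, one extra strip per participant and one retained CO value. Downside: some very light smokers would not be cotinine-positive at baseline and would drop out of the abstinence measure.

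Separately, reconcile the crossover and two-group descriptions, so that it is clear what each participant has received before the follow-up visits.
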